6.3.5. HRQL At-Home Questionnaires

HRQL data obtained from the EQ-5D and DMDSAT will be summarized by treatment group at each visit during overall treatment period based on ITT population.

The EQ-5D questionnaire has two components, health state description and evaluation. The descriptive part consists of health-related quality of life questionnaires covering 5 dimensions (mobility, self-care, usual activities, pain/discomfort, anxiety/depression). Respondents score each dimension, which results in a one-digit number that expresses the level selected (no problems, some problems, extreme problems) for that dimension. In the evaluation part, the respondents evaluate their overall health status using the visual analogue scale (EQ-VAS). The domain scores will be tabulated, and the mean and mean change in EQ-VAS will be summarized by treatment groups at each visit during overall treatment period for ITT population.

The DMDSAT comprised a total of eight questions covering four domains (arm function, mobility, transfers, and ventilation status). The domain scores will be summed up to form the total scores. The domain scores will be tabulated and the mean and mean change in total score will be summarized by treatment groups at each visit during overall treatment period in ITT population.

7. SAFETY EVALUATION

The safety evaluations will be summarized by treatment groups and overall during on-ataluren treatment period based on as-treated-OL population using on-ataluren baseline. By-visit summaries will be provided based on the on-ataluren analysis windows.

7.1. Adverse Events

Adverse events will be coded using the Medical Dictionary for Regulatory Activities (MedDRA). Adverse events will be coded to the MedDRA (Version 24.1 or higher) lower level term closest to the verbatim term. The linked MedDRA PT and primary system organ class (SOC) are also captured in the database. The severity of AEs will be graded using the latest version of the Common Terminology Criteria for Adverse Events (CTCAE), Version 5.0 whenever possible.

A treatment-emergent adverse event (TEAE) during on-ataluren treatment period is defined as an adverse event that occurs or worsens while on ataluren (on or after first dose of ataluren) up to 4 weeks after last dose of ataluren.

Only those AEs that are treatment-emergent will be included in summary tables. All AEs, treatment-emergent or otherwise, will be presented in subject data listings. An overview table of TEAEs, including number of subjects with TEAEs, treatment-emergent serious adverse events (SAEs), deaths, TEAEs classified as CTCAE Grade 3 or higher, study drug related TEAEs, TEAEs leading to study drug withdrawal will be provided for each treatment group. The following summaries will be produced for the TEAEs by treatment group:

- Incidence of TEAEs by SOC and PT
- Incidence of TEAEs by PT in descending order
- Incidence of treatment-related TEAEs by SOC and PT
- Incidence of TEAEs by SOC, PT, and maximum CTCAE grade
- Incidence of TEAEs by SOC, PT, and relationship to treatment.

In the summary tables subjects may be counted under multiple SOC and PTs, but for each SOC and PT, subjects are only counted once. If a subject has the same AE on multiple occasions, the highest severity (5=fatal, 4=life-threatening, 3=severe, 2=moderate, 1=mild) recorded for the event will be presented and the highest drug relationship (1 = 'Unrelated', 2 = 'Unlikely to be Related', 3 = 'Possibly Related', 4 = 'Probably Related'=), reclassified into Related ('Possibly Related', 'Probably Related') or Not Related ('Unrelated'), will be presented on the respective tables. Percentages are based on the number of subjects in the safety population.

The following summaries will also be presented for the treatment-emergent SAEs (TESAEs):

- Incidence of TESAEs by SOC and PT
- Incidence of TESAEs by PT in descending order
- Incidence of treatment-related TESAEs by SOC and PT.

In addition, the number and percentage of subjects with TEAEs and treatment-related TEAEs leading to discontinuation from study treatment will also be summarized by MedDRA SOC and PT for each treatment group.

SAE, AE leading to discontinuation from study treatment, and death will be listed.

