7.4 Describing Adverse Event Relationship to Study Drug

Based on the considerations outlined in [Table 5](#), the investigator should provide an assessment of the relationship of the AE to the study drug, ie, whether there is a reasonable possibility that the study drug caused the AE.

Table 5. Relationship of Study Drug to Adverse Event

Relationship	Description
Probable	A clinical event in which a relationship to the study drug seems probable because of such factors as consistency with known effects of the drug; a clear temporal association with the use of the drug; improvement upon withdrawal of the drug; recurrence upon rechallenge with the drug; lack of alternative explanations for the event.
Possible	A clinical event occurring coincident with administration of the study drug and which may or may not be explained by concurrent disease or other drugs or chemicals. Information on drug withdrawal or rechallenge may be lacking.
Unlikely	A clinical event with a temporal relationship to the study drug exposure that does not preclude causality but for which there is a clear alternate cause that is more likely to have caused the AE than study drug. Such alternatives include a concomitantly administered drug, the subject's disease state, other medical conditions, or environmental factors.
Unrelated	A clinical event for which a relationship to the study drug seems improbable because of factors such as inconsistency with known effects of the study drug, lack of a temporal association with study drug administration, lack of association of the event with study drug withdrawal or rechallenge, and/or presence of alternative explanations for the event. Alternative explanations might include a known relationship of the AE to a concomitant drug, medical history of a similar event, the subject's disease state, other medical conditions, or environmental factors.

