7.1. Adverse Events

AEs will be coded to the MedDRA (Version 24.1 or higher) lower level term closest to the verbatim term. The linked MedDRA PT and primary system organ class (SOC) are also captured in the database. The severity of AEs will be graded using the latest version of the Common Terminology Criteria for Adverse Events (CTCAE), Version 5.0 whenever possible.

For the double-blind treatment period, a treatment-emergent adverse event (TEAE) is defined as an adverse event that:

- Occurs or worsens during the double-blind treatment period (Day 1 to within 4 weeks of last double-blind treatment, and prior to the first open-label treatment) for subjects who complete the double-blind treatment period; and
- Occurs or worsens from the period extending from Day 1 to 4 weeks after the last dose of double-blind study drug for subjects who discontinue from the study early during the double-blind treatment period, or who complete double-blind treatment period but not enroll into open-label treatment period.

Only those AEs that are treatment-emergent will be included in summary tables. All AEs, treatment-emergent or otherwise, will be presented in subject data listings. An overview table of TEAEs, including number of subjects with TEAEs, treatment-emergent serious adverse events (TESAEs), deaths, TEAEs classified as CTCAE Grade 3 or higher, study drug related TEAEs, TEAEs leading to study drug withdrawal will be provided for each treatment group. The following summaries will be produced for the TEAEs by treatment group:

- Incidence of TEAEs by SOC and PT
- Incidence of TEAEs by PT in descending order
- Incidence of treatment-related TEAEs by SOC and PT
- Incidence of TEAEs by SOC, PT, and maximum CTCAE grade
- Incidence of TEAEs by SOC, PT, and relationship to treatment.

In the summary tables subjects may be counted under multiple SOC and PTs, but for each SOC and PT, subjects are only counted once. If a subject has the same AE on multiple occasions, the highest severity (5=fatal, 4=life-threatening, 3=severe, 2=moderate, 1=mild) recorded for the event will be presented and the highest drug relationship (1 = 'Unrelated', 2 = 'Unlikely to be Related', 3 = 'Possibly Related', 4 = 'Probably Related'), reclassified into Related ('Possibly Related', 'Probably Related') or Not Related ('Unrelated', 'Unlikely to be Related'), will be presented on the respective tables.

The following summaries will also be presented for the TESAEs:

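### The open-label SAP puts adverse events rated Unlikely to be Related in neither causality class, while the double-blind SAP counts them as Not Related, so the open-label Not Related counts would be incomplete if programmed as written

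*SAP*

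**What the plan says.** Protocol 7.4 (Table 5) gives investigators four ratings: Probable, Possible, Unlikely and Unrelated. Unlikely is a rating in its own right, for an event whose timing "does not preclude causality but for which there is a clear alternate cause that is more likely to have caused the AE than study drug".

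Both SAPs carry the four levels forward in section 7.1 ("1 = 'Unrelated', 2 = 'Unlikely to be Related', 3 = 'Possibly Related', 4 = 'Probably Related") and show each boy once per SOC and PT at his highest level. They then reduce the four levels to two:

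- Double-blind SAP 7.1: "reclassified into Related ('Possibly Related', 'Probably Related') or Not Related ('Unrelated', 'Unlikely to be Related".
- Open-label SAP 7.1: "reclassified into Related ('Possibly Related', 'Probably Related') or Not Related ('Unrelated", with the Not Related list closing after that single rating.

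Both SAPs plan a table described as "Incidence of TEAEs by SOC, PT, and relationship to treatment" and another described as "Incidence of treatment-related TEAEs by SOC and PT". Open-label SAP 7.1 takes its percentages over the number of subjects in a safety population and puts all AEs in the listings. Under open-label SAP 4.1, safety is summarised from the first ataluren dose, whether double-blind or open-label.

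**The concern.** A two-way split of a four-level scale should give every level a place. The open-label rule leaves one out, and it is a rating that investigators can be expected to use. Relationship to study drug is part of the safety profile named as a secondary endpoint in open-label SAP 2.3.2, so the table concerned reports on a stated endpoint.

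The literal rule also has an odd effect. A boy with one Unrelated episode of a term is counted as Not Related. If he later has an Unlikely episode of the same term, his highest level becomes 2 and he leaves the Not Related row without entering the Related row. A further episode therefore lowers the count.

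If the text stands, the programmer has to decide where level 2 goes: Not Related, Related or missing. The plan should settle that.

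**Working it through.** The plan gives no figure to reproduce, so the check sets the two rules side by side.

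| Level | Rating | Double-blind SAP 7.1 | Open-label SAP 7.1 |
|---|---|---|---|
| 1 | Unrelated | Not Related | Not Related |
| 2 | Unlikely to be Related | Not Related | no class |
| 3 | Possibly Related | Related | Related |
| 4 | Probably Related | Related | Related |

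The double-blind rule assigns 4 of 4 levels and the open-label rule 3 of 4.

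**Effect on counts.** For one SOC or PT line, let n1, n2, n3 and n4 be the numbers of boys whose highest rating is level 1, 2, 3 or 4.

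- Boys with the TEAE: n1 + n2 + n3 + n4.
- Related, both SAPs: n3 + n4.
- Not Related, double-blind rule: n1 + n2. The two classes add to the TEAE total.
- Not Related, open-label rule: n1. The two classes add to n1 + n3 + n4, which is n2 short of the total.

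The Not Related count is therefore low by exactly n2, and the Related count does not move. Percentages are taken over a population and not over classified events, so the Related percentage does not move either. The documents give no n2, so the size cannot be computed.

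**Which outputs are touched.** Only the Not Related rows of the SOC/PT-by-relationship table, and the reconciliation of that table with the TEAE total. The treatment-related TEAE, TESAE and discontinuation tables and the overview count of drug-related TEAEs use only the Related class. The remaining TEAE tables do not use the two-way split.

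**Overlap of the two reports.** The on-ataluren period includes early-start boys' double-blind exposure. An event in that phase whose highest rating is Unlikely would be Not Related in the double-blind report and unclassified in the open-label report.

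**Search for a stated reason.** Open-label SAP section 8 (changes from the protocol) and section 9 (version history) mention no causality rule. Section 8 of the double-blind SAP does not either. The separate document on changes from the planned analysis lists changes to efficacy analyses only.

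**The case against.** The strongest reply is that this is a drafting slip whose intent is plain. A Related/Not Related split is naturally exhaustive. Protocol 7.4 says of an Unlikely event that "there is a clear alternate cause that is more likely to have caused the AE than study drug", which points to Not Related, and the companion SAP says so outright. The same open-label sentence has a stray equals sign after the last rating. The table shells are in a separate document and may already handle level 2 properly. All of this is reasonable, and it limits the claim: the counts would be wrong if the text is programmed as written. It does not remove the defect, because the SAP is the document that sets the derivation.

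Four stronger readings are tempting, and the documents do not support them.

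- *The two periods cannot be compared on causality.* Too broad. Related is defined identically in both SAPs, so the tables built on it are consistent on this point. Only the Not Related rows differ.
- *The drug-related share is overstated.* Suppose, purely as an assumption, that 10% of boy-by-term records are Related, 30% Unlikely and 60% Unrelated. Related as a share of classified records would be 0.10/(0.10 + 0.60) = 14.3% instead of 10%. With 15% Unlikely and 75% Unrelated it would be 0.10/0.85 = 11.8%. The SAP does not tabulate that ratio; on its population denominator the Related percentage is the same under both rules.
- *Affected boys vanish from the safety reporting.* A boy is missing only from a line where his highest rating is Unlikely. He can still appear for other terms, and he remains in the overall TEAE and grade tables and in the listings.
- *The whole 144-week comparison is biased.* Delayed-start boys contribute about 72 weeks on ataluren, both groups fall under the same open-label rule, and the documents give no ground for claiming a bias between them.

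**Conclusion.** The inconsistency is real and its scope is narrow. Open-label SAP 7.1 leaves one of four causality ratings without a class, the double-blind SAP counts that rating as Not Related, and no record shows that a change was intended. If the open-label text is programmed as written, Not Related counts in one table would be too low, that table would not reconcile with the TEAE total, and its Not Related rows would follow a different rule from the double-blind report for some of the same events. That it is a slip rather than a choice is an inference from the wording and the silent change logs.

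The shortfall per line is the number of boys whose highest rating is Unlikely. It is zero if there are none, and otherwise cannot be sized from the documents. No conclusion about drug-related events depends on it. This is a minor point, worth correcting because the rule is wrong as written and the correction is trivial.

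**What to change.** In open-label SAP 7.1, define the second class as the double-blind SAP does: "or Not Related ('Unrelated', 'Unlikely to be Related'), will be presented on the respective tables". All four levels then have a place, each line's Not Related count rises by n2, and Related is unchanged. The cost is one phrase in the SAP and one line in the derivation program, with a check that the table shells agree.

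As a separate editorial point, the same paragraph takes percentages over a safety population that this SAP does not define. Replace it with the population defined in section 3.2, and use one label for that population throughout. Section 3.2 calls it as-treated-OA, while sections 5.1 to 5.3, 5.7, 7, 7.1.1 and 7.2 say as-treated-OL.

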7.1.1. Exposure-Adjusted TEAE

The exposure-adjusted TEAEs will be summarized by treatment group during on-ataluren treatment period for as-treated-OL population as follows:

- Number of subjects with TEAEs and incidence rate per patient-years by SOC and PT
- Number of TEAEs and event rate per patient-years by SOC and PT

For incidence rate, repeated occurrences of an event from the same subject will be counted only once for each subject. For event rate, repeated occurrences of an event from the same subject will be counted per number of occurrences regardless of the subjects. Total patient-years of exposure will be calculated as total duration of ataluren treatment in days divided by 365.25 days.

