2.3. Study Endpoints for Open-Label Treatment Period

The primary and key secondary efficacy endpoints of this study focus on the comparison of ataluren versus placebo in the double-blind treatment period (baseline to Week 72). These endpoints are described in the SAP for the double-blind treatment period.

The efficacy endpoints below focus on the comparison of subjects receiving ataluren from randomization to Week 144 (hereafter will be referred to as early-start ataluren or ataluren/ataluren) versus subjects receiving placebo from randomization to Week 72 and ataluren from Week 72 to Week 144 (hereafter will be referred to as delayed-start ataluren or placebo/ataluren) across the double-blind and open-label treatment periods.

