4. GENERAL CONSIDERATIONS

4.1. Definitions of Treatment Periods

In general, the open-label data analyses will be based on two treatment periods, the overall treatment period and the on-ataluren treatment period.

Overall treatment period: defined as the period from randomization to the end of study, will be used for analyzing and summarizing efficacy endpoints.

On-ataluren treatment period: defined as the period from the first dose of ataluren, regardless of double-blind or open-label ataluren, to the end of the study, will be used for summarizing safety endpoints.

The corresponding baseline for each treatment period is defined in Section 4.3. The corresponding analysis windows are defined in Section 4.9.

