5.2. Duration of Treatment with Study Drug

Duration of treatment with study drug during the overall treatment period will be calculated as:

$$\text{Duration (days)} = \text{Date of last dose of study drug} - \text{Date of first dose of study drug} + 1$$

Duration of treatment with study drug in weeks for the overall treatment period will be summarized continuously and categorically (<24 weeks, 24 weeks to <48 weeks, 48 to <72 weeks, 72 to <96 weeks, 96 to <120 weeks, 120 to <144 weeks, ≥144 weeks) based on ITT population.

Duration of treatment with ataluren during the on-ataluren treatment period will be calculated as:

$$\text{Duration (days)} = \text{Date of last dose of ataluren} - \text{Date of first dose of ataluren} + 1$$

Duration of treatment with ataluren in weeks for the on-ataluren treatment period will be summarized continuously and categorically (<24 weeks, 24 to <48 weeks, 48 to <72 weeks, 72 to <96 weeks, 96 weeks to <120 weeks, 120 to <144 weeks, ≥144 weeks) based on as-treated-OL population.

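### The exposure-adjusted incidence rate counts each boy once but divides by his whole ataluren exposure, so at equal risk the 144-week arm shows lower rates for common events than the 72-week arm

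*SAP*

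**What the plan says.** All references are to the open-label SAP unless stated.

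- **Numerator of the incidence rate (7.1.1):** "For incidence rate, repeated occurrences of an event from the same subject will be counted only once for each subject". The companion event rate counts every occurrence.
- **Denominator (7.1.1):** "Total patient-years of exposure will be calculated as total duration of ataluren treatment in days divided by 365.25 days". No other person-time is defined for either rate.
- **Duration (5.2):** after the words "Duration of treatment with ataluren during the on-ataluren treatment period will be calculated as" comes the formula, last ataluren dose date minus first ataluren dose date plus 1. Nothing in 5.2, 7 or 7.1 ends a subject's time at his first event.
- **Display (7.1.1):** "The exposure-adjusted TEAEs will be summarized by treatment group during on-ataluren treatment period". That period (4.1) is "defined as the period from the first dose of ataluren, regardless of double-blind or open-label ataluren, to the end of the study".
- **The two groups (2.3):** early-start means "subjects receiving ataluren from randomization to Week 144". Delayed-start means "placebo from randomization to Week 72 and ataluren from Week 72 to Week 144".
- **Events that count (7.1):** a treatment-emergent event is one that "occurs or worsens while on ataluren (on or after first dose of ataluren) up to 4 weeks after last dose of ataluren".

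**The concern.** Total exposure is a natural denominator when every occurrence counts, because a subject on treatment can always add another event. It does not fit a count of subjects with at least one event. After his first event of a given term a boy cannot add to the numerator, but his remaining exposure still enlarges the denominator. The displayed rate therefore falls below the true first-event rate, and falls further the longer follow-up runs.

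If both groups had the same follow-up, both columns would shrink alike. Here planned ataluren exposure differs two-fold by design. That difference is the evident reason to adjust for exposure, and for this line the adjustment does not make the columns comparable. A reader could take a lower early-start rate as a sign that adverse events become less frequent with longer treatment, when the denominator alone produced it.

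There is a second, smaller mismatch. Events are counted for 4 weeks after the last dose, but those weeks are not in the denominator. They are a larger share of 72 weeks than of 144.

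**Working it through.** The SAP gives no numerical result for these rates, so there is no figure of its own to reproduce.

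**Inputs.** Planned ataluren exposure (2.3) is 144 weeks = 1,008 days for early-start and 72 weeks = 504 days for delayed-start. Dividing by 365.25 (7.1.1) gives T = 2.760 and 1.380 years. The documents give no adverse event rates, so I assume a constant first-event hazard λ, equal in both groups, and show a range.

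**First-event bias.** Expected displayed incidence rate = (1 − exp(−λT)) / T. Because one T is twice the other, the early/delayed ratio simplifies to (1 + exp(−1.380λ)) / 2 = 1 − p72/2, where p72 is the 72-week risk. It is below 1 for any positive λ and tends to 0.5.

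Example at λ = 0.5 per year:
- early-start: (1 − exp(−1.380)) / 2.760 = 0.748 / 2.760 = 0.271
- delayed-start: (1 − exp(−0.690)) / 1.380 = 0.498 / 1.380 = 0.361
- ratio 0.75

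Rates below are per 100 patient-years. The last column also lets the numerator run 28 days past the last dose, as 7.1 does, assuming full follow-up.

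| True rate per year | 72-week risk | Early shown | Delayed shown | Ratio | Ratio with 4-week tail |
|---|---|---|---|---|---|
| 0.01 | 1.4% | 0.99 | 0.99 | 0.993 | 0.967 |
| 0.05 | 6.7% | 4.67 | 4.83 | 0.967 | 0.941 |
| 0.25 | 29% | 18.1 | 21.1 | 0.854 | 0.832 |
| 0.5 | 50% | 27.1 | 36.1 | 0.751 | 0.733 |
| 1.0 | 75% | 33.9 | 54.2 | 0.626 | 0.614 |

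The true ratio is 1.0 in every row. Absolute rates are also understated in both groups: at 1.0 per year the table would show 34 and 54 instead of 100.

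**Dropout.** A simulation with 400,000 subjects per group and an assumed 5% dropout per 72 weeks, without the 4-week tail, gave ratios of 0.958, 0.838 and 0.636 at 0.05, 0.3 and 1.0 per year. Stopping person-time at the first event gave 0.99, 1.01 and 1.00.

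**Window mismatch in the event rate.** With full follow-up and a constant rate, events accrue over 1,008 + 28 days or 504 + 28 days but are divided by 1,008 or 504. The inflation is 1,036/1,008 = 1.028 (early) and 532/504 = 1.056 (delayed), so the ratio is 1.028/1.056 = 0.974.

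**The case against.** The strongest reply is that little depends on this line. It is descriptive, and no test of these rates is planned. The event rate beside it in 7.1.1 is free of the first-event bias, and 7.1 also tabulates crude subject incidence. Section 2.3 presents the early-versus-delayed contrast as the focus of the efficacy endpoints; the safety endpoint in 2.3.2 is a characterised profile. The placebo-controlled safety comparison is in the separate double-blind SAP (7.1), with 72 planned weeks in both arms. No exposure adjustment is specified for the events of special interest in 7.1.2. Many rows will be rare terms, where the first-event bias is minor: the ratio is at least 0.95 when the 72-week risk is 10% or less. All of this stands and limits the importance of the point. It does not make the denominator right for common preferred terms, whole organ classes or any-event rows.

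Equal constant hazard is also an assumption, and the groups differ in more than exposure. Early-start boys spend their first 72 weeks blinded with 12-weekly visits. Delayed-start boys take ataluren wholly open-label, with 24-weekly visits, 72 weeks further into the study (Protocol Tables 3 and 4). Adverse events are assessed at visits, so detection may differ, possibly in the opposite direction. If first events cluster early, even correct time-at-risk rates over 144 and 72 weeks will differ. This also stands: the ratios above isolate the effect of the denominator and do not predict the observed ratio.

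Two stronger readings are tempting. A reader might infer that the plan would make longer ataluren treatment look safer overall, or that its safety conclusions fail. The documents do not support that, given the unaffected event rate, the crude incidence and the separate placebo-controlled comparison. A reader might also infer that total exposure is simply correct for the event rate. It is not quite, because the counting window runs 4 weeks past the denominator.

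**Conclusion.** The incidence-rate rule is wrong as written: a once-per-subject numerator is divided by exposure that continues after the subject has left the risk set. With planned exposure of 144 versus 72 weeks, the by-group incidence rates are not comparable. At equal constant hazard the early/delayed ratio is 1 − p72/2, from about 0.99 at 0.01 per year to 0.63 at 1.0 per year, with a limit of 0.5. The size rests on constant, equal hazards and planned exposure lengths; modest assumed dropout changes it little.

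The 4-week mismatch is a separate, smaller defect in both rates. For rare terms it is the larger of the two: at 0.01 per year it moves the incidence ratio from 0.993 to 0.967. The event-rate ratio becomes about 0.974.

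This should be corrected before the table is produced, but it is confined to descriptive safety output and does not touch the efficacy conclusions.

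**What to change.** **Incidence rate.** For each organ class and preferred term, define time at risk from first ataluren dose to onset of the first such treatment-emergent event. For a subject with none, end it at the earlier of last dose plus 4 weeks and last study contact. Sum over subjects and divide by 365.25.

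**Event rate.** Keep all occurrences, but end each subject's denominator in the same way, at the earlier of last dose plus 4 weeks and last contact.

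The last-contact limit is needed because post-treatment follow-up is waived for boys who move to another ataluren study or keep post-study access (Protocol Table 4 and 6.2.1.5; open-label SAP 2.1). A flat 4-week extension would count unobserved weeks as event-free, adding up to 28/1,008 = 2.8% to an early-start boy's denominator and 28/504 = 5.6% to a delayed-start boy's.

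**Optional.** If first events are expected to cluster early, also show both groups over their first 72 weeks on ataluren.

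**Cost.** One or two SAP sentences and a derived time-at-risk variable per organ class and preferred term, from data already collected. Incidence rates for common terms will rise. Rates for rare terms and event rates may fall slightly; with full follow-up the event rate is multiplied by 1,008/1,036 = 0.973 (early) and 504/532 = 0.947 (delayed).
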